## PROTOCOL AMENDMENT SUMMARY OF CHANGES TABLE

Document History		
Document	Date	Type of amendment
Amendment 6	18 Jul 2023	Substantial
Amendment 5	09 Feb 2023	Substantial
Amendment 4	19 Oct 2022	Substantial
Amendment 3	14 Jan 2022	Substantial
Amendment 2 a	07 Sep 2021	Substantial
Amendment 1/Addendum C (CN)	21 Jun 2021	Not applicable
Amendment 1/Addendum C (IT)	24 May 2021	Not applicable
Amendment 1/Addendum B (DE)	17 May 2021	Not applicable
Amendment 1/Addendum A (UK)	26 Feb 2021	Not applicable
Amendment 1	04 Dec 2020	Substantial
Original Protocol	31 Jul 2020	Not applicable

a Protocol Amendment 2 was not submitted to all regulatory authorities prior to submission of Protocol Amendment 3. Details of the changes between Protocol Amendment 1 and Protocol Amendment 2 are provided in Section 10.11.

### Amendment 6 (date: 18 Jul 2023)

#### Overall Rationale for the Amendment

The overall rationale for the amendment is to address a request from FDA to re-introduce certain safety assessments to support the safety profile of rozanolixizumab in a new population. Since Amendment 5, there has been no change in the benefit/risk profile of rozanolixizumab.

Minor grammatical, editorial, and formatting changes have also been made for clarification purposes only.

This amendment is considered to be substantial based on the criteria set forth in Article 10(a) of Directive 2001/20/EC of the European Parliament and the Council of the European Union.

Section # and Name	Description of Change	Brief Rationale
1.1 Synopsis 1.3 Schedule of activities 3 Objectives and Endpoints 8.9.1 Immunology 9.4.2.4 Immunological analyses 10.2 Appendix 2 Clinical laboratory tests	Endpoints, procedures, and text relating to the assessment of serum [REDACTED] concentrations reinstated as per Protocol Amendment 3.	As per FDA request.

Section # and Name	Description of Change	Brief Rationale
1.1 Synopsis 4.1 Overall design 6.8 Treatment after the end of the study	Protocol sections updated with part or all of the following text: Study participants who complete the 24-week Treatment Period and require further treatment may have the option to access rozanolixizumab via another clinical study or an access program, if available, as per local laws and regulations. Study participants continuing with rozanolixizumab must complete an End of Treatment Visit and be transitioned to rozanolixizumab provided by those alternative options without undergoing SFU or EOS Visits.	To facilitate plans for optional post-trial access to rozanolixizumab, where applicable.
1.3 Schedule of activities 5.2 Exclusion criteria 7.1.2 Permanent discontinuation due to other AEs 10.2 Appendix 2 Clinical laboratory tests	The IGRA TB test was re-instated as a Screening procedure as per Protocol Amendment 4, with exclusion criterion #11 updated to exclude participants with a positive TB test at Screening unless the positive test result is related to adequately treated latent TB infection. Footnote j of Table 1-1 updated to include a cross-reference to Section 10.12. Protocol updated to indicate that participants with LTBI at Screening can be randomized after undergoing 4 weeks of TB prophylactic treatment. Exclusion criterion #12 re-instated to that used in Protocol Amendment 4 to exclude participants with LTBI (unless prophylaxis initiated 4 weeks prior to first dose of IMP) and participants with current or a history of NTM infection (unless fully recovered). Section 7.1.2 updated to state that participants who develop active TB, LTBI, or NTM infection must be permanently discontinued from IMP.	As per FDA request.

Section # and Name	Description of Change	Brief Rationale
1.3 Schedule of activities	Vital sign assessments re-instated at Week 17 and Week 21 (Visits 22 and 26) and removed from Week 22 (Visit 27).	Correction.
5.2 Exclusion criteria	Exclusion criterion #6 re-instated as per Protocol Amendment 4.	As per FDA request.
5.2 Exclusion criteria	Exclusion criterion #8b (previously #8a) updated to exclude participants with a serious infection 6 weeks prior to the first dose of IMP.	As per FDA request.
5.2 Exclusion criteria	Exclusion criterion #15 (excluding participants with an [REDACTED] deficiency) re-instated as per Protocol Amendment 4.	As per FDA request.
6.5.2 Prohibited prior and concomitant treatments (medications and therapies)	Any use of cyclophosphamide prior to the Baseline visit is prohibited (re-instatement of Protocol Amendment 4 timeframe)	As per FDA request.
7.1.2 Permanent discontinuation due to other AEs	The phrase 'and move to the Safety Follow-up Period' was removed as the procedure is better described in Section 7.1.	For clarity.
8 Study assessments and procedures	Text in penultimate paragraph updated to indicate that unscheduled assessments (as well as unscheduled visits) can be performed at the investigator's discretion.	To remind investigators that safety assessments can be performed if required.
9.3 Planned efficacy/outcome analyses	Text describing the additional adjustments to be made to the statistical modelling to accommodate prior disease-related therapies has been removed from Section 9.3.	Details of subgroup analyses based on prior treatment will be provided in the SAP.
9.3.2 Secondary efficacy analysis	Clarified that there are 4 alpha-controlled secondary endpoints	As per FDA request.
9.3.3.2 Seizure control	Added text that defines seizure count categories.	For clarity.
10.3 Appendix 3: Adverse Events – Definitions and Procedures for Recording, Evaluating, Follow-up and Reporting	Text added to remind investigators that safety reporting requirements for the TB are provided in Section 10.12	For clarity.

Section # and Name	Description of Change	Brief Rationale
10.12.2 Screening Period 10.12.3 Physical examination 10.12.4 Interferon gamma release assay (IGRA) 10.12.5 Practical steps 10.12.7 Latent TB 10.12.8 Active TB	Text revised to require participants with LTBI undergo 4 weeks (instead of 1 week) of TB prophylactic treatment prior to randomization. The removal of the possibility for participants to remain receiving IMP in the event of a new diagnosis of LTBI.	To align with changes made in the body of the protocol.

This document cannot be used to support any marketing application and any extensions or variations thereof.  
PUBLIC COPY

## 1 PROTOCOL SUMMARY

### 1.1 Synopsis

**Protocol title:** A randomized, double-blind, placebo-controlled, multicenter, Phase 2 study to evaluate the efficacy, safety, and pharmacokinetics of rozanolixizumab in adult study participants with leucine-rich glioma inactivated 1 autoimmune encephalitis

**Short title:** A Phase 2 study evaluating the efficacy and safety of rozanolixizumab in participants with leucine-rich glioma inactivated 1 autoimmune encephalitis

**Rationale:** Autoimmune encephalitis (AIE) is a group of disorders where the immune system causes inflammation of the brain, leading to debilitating neurological and psychiatric symptoms. There are currently no approved treatments for AIE. Leucine-rich glioma inactivated 1 AIE (LGI1 AIE) has a distinct clinical presentation and has been identified as a variant that may be suitable for immunotherapy, and therefore for treatment with rozanolixizumab, which blocks the activity of neonatal Fc receptor (FcRn), accelerates the catabolism of antibodies and reduces the concentration of immunoglobulin (Ig) G.

### Objectives and Endpoints

Objectives	Endpoints
Primary	
• To assess the efficacy of rozanolixizumab as measured by seizure freedom	• Seizure freedom (defined by 28 consecutive days of no seizures) maintained until the end of the Treatment Period (Week 25)
Secondary	
• To assess the efficacy of rozanolixizumab as measured by a change in cognitive function	• Change from Baseline in Repeatable Battery for the Assessment of Neuropsychological Status (RBANS) total scale index score at the end of the Treatment Period (Week 25)
• To assess the efficacy of rozanolixizumab on study participants' overall disability	• Proportion of participants with a favorable outcome in the Modified Rankin Scale (mRS) during the Treatment Period, where favorable outcome is defined as no worsening for participants with a Baseline mRS score of $\leq 1$ or improvement of $\geq 1$ point for participants with a Baseline mRS score of $\geq 2$
• To assess the efficacy of rozanolixizumab as measured by use of rescue medication	• Use of rescue medication due to an absence or loss of clinical benefit during the Treatment Period

Objectives	Endpoints

• To assess the efficacy of rozanolixizumab as measured by the onset of seizure freedom

	

• Time to first occurrence of seizure freedom (TTSF) defined by the number of days after randomization to the first day of the first 28 consecutive days without seizures during the Treatment Period

• To assess the safety and tolerability of rozanolixizumab

	

• Incidence of treatment-emergent adverse events (TEAEs) during the study

Exploratory	

• To assess the time of onset of efficacy of rozanolixizumab for the subgroup of study participants who achieve the primary endpoint as measured by the onset of seizure freedom

	

• Time to achieving seizure freedom (defined by 28 consecutive days of no seizures) maintained until the end of the Treatment Period (Week 25)



• To assess the efficacy of rozanolixizumab as measured by seizure control

	

• ‘Good’ or ‘Moderate’ seizure control maintained over a period of 4 consecutive weeks until the end of the Treatment Period (Week 25)

• To assess the efficacy of rozanolixizumab as measured by a change in cognitive function (domains of RBANS)

	

• Change from Baseline in the domain scores of RBANS (immediate memory; visuospatial/constructional; delayed memory; language; and attention) during the Treatment Period

• To assess the efficacy of rozanolixizumab using an integrated ranked analysis of combined clinical and functional outcome measures

	

• Ranked outcome derived from the combined integrated analysis of clinical and functional assessments (including mRS, seizure freedom, and, cognitive function) at the end of the Treatment Period (Week 25)

• To assess the safety and tolerability of rozanolixizumab

	

• Change from Baseline in vital signs and laboratory results during the study

• To assess the pharmacodynamic (PD) effect of rozanolixizumab as measured by the total IgG concentrations in serum

	

• Value and change (absolute and percentage) from Baseline in serum total IgG and IgG subclass concentrations during the study

Objectives	Endpoints

To assess the PD effect of rozanolixizumab as measured by LGI1 autoantibody levels using the flow cytometry LGI1 quantitative assay

	

Value and change from Baseline in LGI1 autoantibody serum levels during the Treatment Period

Value and change from Baseline in LGI1 autoantibody cerebrospinal fluid (CSF) levels during the Treatment Period (for consenting participants)



To evaluate the effects of rozanolixizumab on patient-reported health-related quality of life (HRQoL)

	

Value and change from Baseline in the 36-item Short Form Survey (SF-36) Physical Component Summary (PCS) score, Mental Component Summary (MCS) score, and individual domain scores during the Treatment Period

Value and change from Baseline in the EuroQol-5D-5L (EQ-5D-5L) during the Treatment Period

Value and shift from Baseline in Clinical Global Impression of Severity (CGI-S) during the Treatment Period

To evaluate the effects of rozanolixizumab on healthcare resource utilization (HCRU)

	

Disease-related hospitalizations (number, duration)

To assess the pharmacokinetic (PK) characteristics of rozanolixizumab

	

Plasma concentration of rozanolixizumab during the Treatment Period

To evaluate the impact of concomitant antiepileptic drugs (AEDs) on rozanolixizumab plasma levels

	

Plasma concentration of rozanolixizumab during the Treatment Period

To evaluate the incidence and emergence of antidrug antibody (ADA) of rozanolixizumab and impact on PK and PD

	

ADA status

Objectives	Endpoints

To evaluate the effects of rozanolixizumab on the concentration of total protein, albumin, [REDACTED] and serum and plasma complement levels

	

Values and change from Baseline in total protein, albumin, and serum immunoglobulin concentrations ([REDACTED] during the Treatment Period

Values and change from Baseline in serum complement levels ([REDACTED]), and plasma complement levels ([REDACTED]) in case of infusion or hypersensitivity reaction



To assess exploratory biomarkers

	

Deoxyribonucleic acid (DNA), ribonucleic acid (RNA), and genetic analysis that may be measured to understand the cause and appropriate treatment of LGI1 AIE

Exploratory biomarkers such as but not limited to [REDACTED] [REDACTED]

Proteins and metabolite changes may be measured to understand the cause, progression, and appropriate treatment of LGI1 AIE

## Overall Design

This is a Phase 2, multicenter, randomized, double-blind, placebo-controlled, 2-arm, repeat dose study to evaluate the efficacy, safety, and PK of rozanolixizumab for the treatment of LGI1 AIE.

Approximately 68 adult study participants with LGI1 AIE with onset of disease symptoms between 0 to 12 months prior to study entry, as assessed by the investigator, will be randomized to receive rozanolixizumab [REDACTED] or placebo, administered by subcutaneous (sc) infusion at [REDACTED] intervals for 24 weeks. A Treatment Period of 24 weeks has been selected to ensure a sufficient time period to evaluate a difference between rozanolixizumab and placebo in key symptoms of the disease. The primary objective of the study is to assess the efficacy of rozanolixizumab as measured by seizure freedom.

Down titration of steroids will begin after at least 3 days on the initial high dose corticosteroids (based on the decision of the investigator).

The study participants will be stratified at randomization by:

- Time from disease symptom onset ( $\leq 6$  months or  $> 6$  months from disease symptom onset)
- Cognitive function (RBANS score of  $\leq 85$  or  $> 85$ )

After the initial 5 investigational medicinal product (IMP) administrations have been performed at the clinic (if applicable), the study participant may have the opportunity to be treated at home by a visiting healthcare practitioner.

Although the use of rescue medication is allowed at any time during the study, the use of rescue medications should be delayed, if clinically feasible, for at least 4 weeks following the initiation of study treatment. Study participants who require use of rescue medication will discontinue blinded treatment and complete the assessments for the Early Discontinuation (EDisc) Visit. Following this, the selection of an appropriate rescue medication will be made at the investigators discretion, and the study participant will enter the Safety Follow-Up (SFU) Period. Unscheduled study visits are permitted for any study participant including those study participants who have initiated rescue medication.

An Independent Data Monitoring Committee (IDMC) will be established for the study to monitor the emerging safety data within the clinical study on a periodic basis.

### **Number of Participants**

To account for an expected 10% dropout rate within each treatment arm, approximately 68 participants will be randomly assigned to study treatment arms such that approximately 60 evaluable study participants complete the study.

### **Treatment Groups and Duration**

The maximum study duration per study participant is upto 38 weeks. There are 3 study periods:

- Screening Period: Eligibility will be assessed during the Screening Period of up to 42 days. If a study participant becomes seizure free as a result of steroid treatment, the participant may still be randomized in the study, providing the prior occurrence of seizures is well documented.

Following screening and completion of the Baseline assessments, treatment will be initiated in study participants who are deemed appropriate for initiation or re-initiation of high dose corticosteroids (500 to 1000mg methylprednisolone [MP] equivalent /day) based on clinical symptoms and history, or who have initiated corticosteroids within 42 days prior to randomization at a dose of 500 to 1000mg MP equivalent/day. Corticosteroids can be initiated prior to the start of the Screening Period, however, the study participant must be randomized within 42 days of corticosteroids initiation. If the study participant has initiated a steroid taper, the study participant cannot receive oral steroids at a dose lower than 40mg/day when randomized. Study participants receiving a steroid dose of 60mg/day, 50mg/day or 40mg/day at the time of randomization, will have to maintain that dose for 7 days ( $\pm 2$  days), 14 days ( $\pm 2$  days) or 21 days( $\pm 2$  days), respectively, before resuming [REDACTED] down-titration steps. Each subsequent down-titration step will last for 7 days ( $\pm 2$  days; see Section 1.2). For those participants that have not initiated a steroid taper, the down-titration of the oral steroid dose will begin after at least 3 days on the initial high dose corticosteroids, as per investigator' discretion.

- Treatment Period: Participants who have been confirmed eligible will be randomized in a 1:1 ratio to receive rozanolixizumab [REDACTED] or placebo at [REDACTED] intervals over a 24-week Treatment Period. Initially, study participants will receive rozanolixizumab or placebo in addition to intravenous (iv) or oral steroids that will be tapered as described in Section 1.2.
- Safety Follow-Up Period: Study participants who complete the 24-week Treatment Period or prematurely discontinue IMP, as well as study participants who receive rescue medication during the 24-week Treatment Period will undergo the End of Treatment (EOT) Visit/EDisc

[figure not shown]
Visit and enter the SFU Period. At 4 weeks after the final dose, study participants will undergo a SFU phone call, and at 8 weeks after the final dose, study participants will undergo the End of Study (EOS) Visit.

Study participants who complete the 24-week Treatment Period and require further treatment may have the option to access rozanolixizumab via another clinical study or an access program, if available, as per local laws and regulations. Study participants continuing with rozanolixizumab must complete an End of Treatment Visit and be transitioned to rozanolixizumab provided by those alternative options without undergoing SFU or EOS Visits.

This document cannot be used to support any marketing application and any extensions or variations thereof.

PUBLIC COPY

## 1.2 Schema

EDisc=early discontinuation; EOT=end of treatment; EOS=end of study; MP=methylprednisolone; SFU=safety follow-up; W=Week

Note: Rozanolixizumab or placebo will be initiated in study participants who are deemed appropriate for initiation or re-initiation of corticosteroids based on clinical symptoms and history, or have initiated corticosteroids within 42 days prior to randomization at a dose of 500 to 1000mg MP equivalent/day. Study participants will be administered rozanolixizumab or placebo in addition to iv or oral steroids that will be tapered. The dotted line indicates the period in which each down-titration step may occur.

Note: Visit 17 and Visit 18 were removed in Protocol Amendment 4 and Visit 4 was removed in Protocol Amendment 5; however, the Visits were not renumbered.

### 1.3 Schedule of activities

The Schedule of Activities is provided in [Table 1-1](#). Visit 32 (Week 25) is designated as the EOT Visit however, study participants that undergo early discontinuation will undergo these assessments as part of the EDisc Visit, which may occur at any week of Treatment Period. Study participants who undergo the EDisc Visit should then follow the same temporal schedule for subsequent visits (ie, complete the SFU phone call and EOS Visit at 3 and 7 weeks after the EDisc Visit, respectively).

Some study-specific investigations may not be conducted according to the study protocol during a pandemic or other exceptional circumstances due to the need to implement safety measures and guidance from regulatory authorities (see [Section 8](#) for further information).

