j The IGRA test will be performed by a local laboratory. Study participant should not be dosed in case of any positive IGRA or 2 indeterminate IGRA until the study participant has been evaluated by a TB specialist. Further details are provided in Section 10.12.

k Vital signs comprise systolic and diastolic BP, pulse rate, and temperature.

l The interval between administration of 2 consecutive rozanolixizumab doses should be  $7 \pm 2$  days. On dosing days for the first 2 weeks (Visit 2 and Visit 5), a 4-hour post-dose observation will be in place. Assuming the first 2 doses were well tolerated, on dosing days in Week 3, 4, and 5 (Visit 6, Visit 7, and Visit 8), a 1-hour post dose observation will be in place. Assuming the first 5 doses were well tolerated, on subsequent weeks, a 15-minute post-dose observation will be in place. Following a missed dose due to temporary IMP discontinuation, a 1-hour observation will be in place for the first 2 doses followed by a 15 minute observation per above. The minimum post dose observation time frame may be extended at the discretion of the investigator or study nurse at home dosing visits. These recommendation are applicable for dosing at site and at home except where specified.

m At Visits 2, 8, 12, 16, 22, and 29, blood samples for PK will be obtained predose. At nondosing Visits 3, 30, 31, and 32, samples will be obtained once during the visit.

n Serum and plasma complements are to be obtained predose at Baseline (Day 1) for all study participants.

o Ad hoc assessments of IgG and albumin can be performed to monitor the recovery of IgG and albumin levels, or for random sampling of study participants to maintain the blind. These results will be reviewed by the unblinded medical monitor only (Section 7.1.4).

p For Visits 9–11, Visits 13–15, Visits 19–21, and Visits 23–25, samples for total IgG assessments are only required to be taken at the middle visit (ie, Visits 10, 14, 20, and 24). In the table, the samples required at these visits are described as '-/X/-' representing no sample (-)/sample (X)/no sample (-).

q For study participants who withdraw from the study, a sample should be taken for ADA analysis upon his/her EDisc Visit. A Screening sample will be taken for the purpose of assay parameter characterization (eg, setting ADA cut points and PK selectivity assessments).

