- The participant is considered to have been under treated in the opinion of the investigator

AND

- Currently the participant is experiencing a seizure rebound that requires initiation or re-initiation of high dose corticosteroids (500-1000mg MP equivalent /day) in the opinion of the investigator.

Following screening and completion of the Baseline assessments, treatment will be initiated in study participants who are deemed appropriate for initiation or re-initiation of high dose corticosteroids (500 to 1000mg MP equivalent/day) based on clinical symptoms and history, or who have initiated corticosteroids within 42 days prior to randomization at a dose of 500 to 1000mg MP equivalent/day. Corticosteroids can be initiated prior to the start of the Screening Period, however, the study participant must be randomized within 42 days of corticosteroids initiation. If the study participant has initiated a steroid taper, the study participant cannot receive oral steroids at a dose lower than 40mg/day when randomized. Study participants receiving a steroid dose of 60mg/day, 50mg/day or 40mg/day at the time of randomization will have to maintain that dose for 7 days ( $\pm 2$  days), 14 days ( $\pm 2$  days) or 21 days( $\pm 2$  days), respectively, before resuming [REDACTED] down-titration steps. Each subsequent down-titration step will last for 7 days ( $\pm 2$  days; see Section 1.2). For those participants that have not initiated a steroid taper, the down-titration of the oral steroid dose will begin after at least 3 days on the initial steroid dose, as per investigator.

- Treatment Period: Participants who have been confirmed eligible will be randomized in a 1:1 ratio to receive rozanolixizumab [REDACTED] or placebo at [REDACTED] intervals over a 24-week Treatment Period. Initially, study participants will receive rozanolixizumab or placebo in addition to iv or oral steroids that will be tapered as described in Section 1.2.
- Safety Follow-Up Period: Study participants who complete the 24-week Treatment Period or prematurely discontinue IMP, as well as study participants who receive rescue medication during the 24-week Treatment Period will undergo the EOT Visit/EDisc Visit and enter the SFU Period. At 4 weeks after the final dose, study participants will undergo a SFU phone call, and at 8 weeks after the final dose, study participants will undergo the EOS Visit.

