#### **4.4 End of study definition**

A study participant is considered to have completed the study if he/she has completed all phases of the study, including the SFU Period. Study participants will have an EOT Visit performed 1 week after the final dose of IMP or upon discontinuation of the study, followed by a SFU phone call 4 weeks after and an EOS Visit 8 weeks after the final dose.

The end of study is defined as the date of the last visit of the last study participant in the study.

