### **6.5.3      Rescue medication**

Rescue medication considered most appropriate for the study participant will be selected by the investigator. The study site will supply rescue medication that will be obtained locally. The effect of rozanolixizumab on the efficacy of IgG biologics and Fc-fusion proteins is not known.

Although the use of rescue medication is allowable at any time during the study, the use of rescue medications should be delayed, if clinically feasible, for at least 4 weeks following the initiation of study treatment. Study participants who require rescue medication will discontinue blinded treatment, and complete the assessments for the Edisc Visit. Following this, the selection of an appropriate rescue medication will be made at the investigator's discretion, and the study participant will enter the SFU Period during which unscheduled visit' may be performed. Rescue medications are permitted during the SFU Period.

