### **10.12.8 Active TB**

Study participants who develop active TB during the study must be immediately permanently discontinued from study medication and a EDisc Visit must be scheduled as soon as possible, but no later than the next scheduled visit. The study participant should be encouraged to keep the End of Study Visit as specified by the protocol. Treatment for active TB should be started immediately.

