- Safety Follow-Up Period: Study participants who complete the 24-week Treatment Period or prematurely discontinue IMP, as well as study participants who receive rescue medication during the 24-week Treatment Period will undergo the End of Treatment (EOT) Visit/Early Discontinuation Visit and enter the SFU Period. At 4 weeks after the final dose, study participants will undergo a SFU phone call, and at 8 weeks after the final dose, study participants will undergo the End of Study (EOS) Visit.

A schematic of the study design is provided in [Figure 1-1](#).

Figure 1-1: Study schematic

EDisc=early discontinuation; EOT=end of treatment; EOS=end of study; MP=methylprednisolone; SFU=safety follow-up; W=Week

Note: Rozanolixizumab or placebo will be initiated in study participants who are deemed appropriate for initiation or re-initiation of corticosteroids based on clinical symptoms and history, or have initiated corticosteroids within 42 days prior to randomization at a dose of 500 to 1000mg MP equivalent/day. Study participants will be administered rozanolixizumab or placebo in addition to iv or oral steroids that will be tapered. The dotted line indicates the period in which each down-titration step may occur.

Note: Visit 17 and Visit 18 were removed in Protocol Amendment 4 and Visit 4 was removed in Protocol Amendment 5; however, the Visits were not renumbered.

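### For early discontinuers, protocol 1.3 counts the last two safety contacts from the EDisc Visit while 1.1, 4.1, 4.4 and SAP 1.2 count them from the final dose; if EDisc is less than 7 days after the last dose, EOS falls before the 56-day TEAE window closes

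*Protocol*

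**What the plan says.** Protocol 1.3 tells participants who have an EDisc Visit to keep the same spacing as completers, that is, to "complete the SFU phone call and EOS Visit at 3 and 7 weeks after the EDisc Visit, respectively". It lets EDisc fall in any week of the Treatment Period.

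The protocol synopsis (1.1, Treatment Groups and Duration) counts from dosing: "At 4 weeks after the final dose, study participants will undergo a SFU phone call". Section 4.1 gives the matching rule for the last visit: "at 8 weeks after the final dose, study participants will undergo the EOS Visit". SAP 1.2 repeats it: "at 8 weeks after the final dose, study participants will undergo the End of Study (EOS) Visit". In all three places the sentence follows one that names participants who stop IMP prematurely or receive rescue medication, so it is not limited to completers. Section 4.4 also gives 4 and 8 weeks from the final dose, after an "EOT Visit performed 1 week after the final dose of IMP or upon discontinuation of the study".

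Three other statements matter:

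- Protocol 8.3.1 collects adverse events up to the EOS Visit, and serious events for a further 30 days after each participant's end of study.
- SAP 5.6.2.1 closes the TEAE window 8 weeks (56 days) after the final dose.
- Protocol 7.1.4 allows temporary holds of IMP and states no maximum length.

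**The concern.** A site with an early discontinuer has two dates for the same last safety visit, and no text says which prevails. A monitor could call one EOS date compliant under 1.3 and a deviation under 4.1.

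The dates part whenever EDisc is not 7 days after the last dose. Several passages allow or point to an earlier EDisc. Section 4.4 lets the visit take place on discontinuation. For active TB, section 10.12.8 says an "EDisc Visit must be scheduled as soon as possible, but no later than the next scheduled visit". Section 6.5.3 puts EDisc ahead of rescue treatment ("Following this, the selection of an appropriate rescue medication will be made"), which is a reason not to wait.

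TEAE incidence is a secondary endpoint. If EOS comes before day 56, routine collection stops while the analysis window is still open, and no later contact is scheduled. Only discontinuers are exposed to this, and they include people who stopped for safety reasons.

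**Working it through.** **Inputs.** Protocol 1.3: call at EDisc + 21 days, EOS at EDisc + 49 days. Protocol 1.1, 4.1, 4.4 and SAP 1.2: call at final dose + 28 days, EOS at final dose + 56 days. SAP 5.6.2.1: TEAE window closes at final dose + 56 days. Table 1-1, footnote l: "The interval between administration of 2 consecutive rozanolixizumab doses should be" 7 ± 2 days, so the next dosing visit is 5 to 9 days after the last dose. Protocol 8.3.1: serious events for 30 days after the end of study, taken here as the EOS Visit.

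**Formulas.** Let g be the days from last dose to EDisc (or EOT). Under 1.3, call = g + 21 and EOS = g + 49, in days after the last dose. Days of the TEAE window left after EOS = max(0, 56 - (g + 49)) = max(0, 7 - g).

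**The plan's own figures.** The scheduled EOT has g = 7, which gives 7 + 21 = 28 and 7 + 49 = 56. The 4 and 8 weeks reproduce exactly, so completers are unaffected. The 3 and 7 weeks in 1.3 are this completer spacing carried over to EDisc.

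**Early discontinuers (days after last dose).**

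| g | Call, 1.3 | EOS, 1.3 | Call / EOS, final-dose rule | Window left after EOS under 1.3 | Call / EOS, later of the two |
|---|---|---|---|---|---|
| 0 | 21 | 49 | 28 / 56 | 7 | 28 / 56 |
| 5 | 26 | 54 | 28 / 56 | 2 | 28 / 56 |
| 6 | 27 | 55 | 28 / 56 | 1 | 28 / 56 |
| 7 | 28 | 56 | 28 / 56 | 0 | 28 / 56 |
| 9 | 30 | 58 | 28 / 56 | 0 | 30 / 58 |
| 14 | 35 | 63 | 28 / 56 | 0 | 35 / 63 |
| 28 | 49 | 77 | 28 / 56 | 0 | 49 / 77 |

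At the next dosing visit (g = 5 to 9) the gap is 0 to 2 days, at most 2/56 = 3.6% of the window. The upper bound, EDisc on the dosing day, is 7/56 = 12.5%. Serious-event reporting ends on day g + 49 + 30 = g + 79, so it always passes day 56.

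**The other direction.** Changing 1.3 to the final-dose rule alone moves EOS by 56 - (g + 49) = 7 - g days: 2 days earlier at g = 9, 7 earlier at g = 14, 21 earlier at g = 28. The call then falls 28 - g days after EDisc: on the EDisc day at g = 28, and before it for larger g. Values above 9 can occur because 7.1.4 and 10.13 allow holds with no stated maximum, and a participant may stop for good without restarting.

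**The case against.** The best defence is that 1.3 is loose wording and not a competing rule: it presents its figures as the ordinary schedule, and for the scheduled EOT they are right. In the usual case the gap is at most 2 days. Any visit window in the Table 1-1 header, which is not legible in the available text, could absorb that.

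Support for a very early EDisc is also limited. The words in 4.4 concern leaving the study, and under 7.2.1 participants withdrawn from the study are only encouraged to enter follow-up. Section 6.5.3 gives an order of events but no interval. Only the active TB text asks for speed, and no passage describes g = 0. The 7-day figure is therefore a bound and not an expected value.

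The SAP's 56-day limit says which events are not TEAEs; it does not oblige sites to collect through day 56, so an EOS on day 54 breaks no stated analysis rule. Section 8.3.1 also asks for events in the post-treatment periods that the protocol requires. Finally, 7.1.3, 7.2.1 and 8.3.5 describe an 8-week follow-up entered at EDisc, and the SAP's study-period definitions start that period the day after the Treatment Period ends, so the final-dose anchor is not used uniformly.

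All of this reduces the size of the point. It does not remove the conflict: 1.1, 4.1 and SAP 1.2 expressly apply the final-dose timing to premature discontinuers, and nothing fixes EDisc at day 7.

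**Conclusion.** The inconsistency is certain and its effect is minor. When g is below 7, a site that follows 1.3 may not collect new non-serious adverse events in the last 7 - g days of the TEAE window: up to 2 days at the next dosing visit, 7 at most. When g is 7 or more there is no gap in the window.

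Two stronger readings are tempting. A reader might infer that serious events go uncollected or that the safety comparison is materially biased. The documents do not support this: serious events are reported for 30 more days, completers are unaffected, and only early discontinuers among the 12 participants reported in SAP section 3 can be touched. Their number is not given. A reader might also infer that 1.3 is simply wrong and should copy the final-dose rule. That fails for g above 7, where the EDisc anchor is the one that protects follow-up after the visit.

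The size rests on nominal days with no visit window applied. SAP section 1 says that nobody was randomized under the current amendment, and the documents do not show whether earlier protocol versions carried the same sentence in 1.3.

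**What to change.** In 1.3, state that for early discontinuers the SFU phone call takes place 3 weeks after EDisc or 4 weeks after the final dose of IMP, whichever is later, and the EOS Visit 7 weeks after EDisc or 8 weeks after the final dose, whichever is later. Put the same rule for early discontinuers into 1.1, 4.1 and 4.4; SAP 1.2 repeats their sentence and should follow.

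This takes every EOS to day 56 or beyond and keeps the call at least 3 weeks after EDisc. The cost is a few short wording edits and an EOS Visit up to 7 days later than 1.3 now gives when g is below 7. For g of 7 or more, the dates in 1.3 do not change. No visit is added.

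Recruitment has stopped, so if no further amendment is made, the sponsor can compare each early discontinuer's EOS date with last dose + 56 days and report any shortfall in the clinical study report.
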